2.4 Primary Endpoint

• Changes in the mean daily Numerical Rating Scale (NRS) scores for the worst endometriosis-related pain at cycle 4

2.5 Secondary Endpoints

- Changes in the mean daily NRS scores for the worst endometriosis-related pain on days with menstrual bleeding (i.e. dysmenorrhea) and for the worst endometriosis-related pain on days with no menstrual bleeding (i.e. non-menstrual pelvic pain) at cycle 4
- Changes in the mean daily NRS scores for the worst endometriosis-related pain over 8 menstrual cycles

- Changes in the mean daily NRS scores for the worst dysmenorrhea over 8 menstrual cycles
- Changes in the mean daily NRS scores for the worst non-menstrual pelvic pain over 8 menstrual cycles
- Changes in the mean daily NRS scores for the worst dyspareunia on days with sexual intercourse over 8 menstrual cycles
- Frequency of avoiding sexual intercourse due to expected pain over 8 menstrual cycles
- Changes in the mean daily NRS scores for the worst impact of endometriosis-related pain on the subject's ability to function over 8 menstrual cycles
- Changes in the mean weekly scores of the Endometriosis Health Profile-30 (EHP-30) pain impact domain over 8 menstrual cycles
- Changes in vaginal bleeding pattern over 8 menstrual cycles
- Percentage of days with mild and/or strong rescue analgesics used over 8 menstrual cycles
- Total and average doses of mild and/or strong rescue analgesics used over 8 menstrual cycles
- Responder rate assessed as ≥30%, ≥50% and ≥70% reduction from the baseline in mean daily NRS score for the worst endometriosis-related pain, dysmenorrhea and non-menstrual pelvic pain and for the worst endometriosis-related pain impact, over 8 menstrual cycles
- Changes in the mean individual and total symptom and sign severity scores of the Biberoglu and Behrman (B&B) scale at cycles 4 and 8
- Changes in the EHP-30 scores over 8 menstrual cycles
- Changes in Patient Global Impression of Severity (PGIS) scores at cycles 4 and 8
- Patient Global Impression of Change (PGIC) scores at cycles 4 and 8
- Plasma concentration of quinagolide and metabolites during cycles 1, 4 and 8
- Serum levels of mid-luteal phase progesterone at cycles 1, 4 and 8
- Proportion of subjects with serum levels of mid-luteal progesterone ≥25 nmol/L (7.9 ng/mL) at cycles 1, 4 and 8
- Serum levels of mid-luteal estradiol, prolactin, thyroid-stimulating hormone (TSH) and insulin-like growth factor-1 (IGF-1) at cycles 1, 4 and 8
- Changes in bone turnover markers, determined by bone resorption marker serum Cterminal cross-linking telopeptide of type 1 collagen (s-CTx) and bone formation marker serum procollagen type I N propeptide (s-PINP) at cycles 4 and 8
- Changes in ECG parameters including PR interval, QT interval, corrected QT using Fridericia's formula (QTcF) and QRS interval at cycles 4 and 8
- Proportion of subjects with abnormal clinically significant echocardiography findings indicating valvular heart disease at cycles 4 and 8
- Proportion of subjects identified with potential impulse control disorders by the questionnaire for impulsive-compulsive disorders at cycles 4 and 8
- Frequency and intensity of adverse events

Statistical Analysis Plan	Version: 1.0	FERRING
Quinagolide	31MAY2022	PHARMACEUTICALS
FE 999051 trial 000165	CONFIDENTIAL	Page 9 (44)

- Changes in circulating levels of clinical chemistry and hematology parameters, urinalysis parameters, and proportion of subjects with markedly abnormal changes
- Frequency and intensity of ring acceptability parameters over 8 menstrual cycles

2.6 Exploratory Endpoint

Changes in endometriosis biomarkers such as serum levels of VEGF, placenta growth factor (PlGF), interleukin 6 (IL-6) and soluble fms-like tyrosine kinase 1 (sFlt-1) at cycles 4 and 8.

3 Trial design

This is a randomized, double-blind, placebo-controlled, phase 2 trial assessing the efficacy, safety and dose-response of quinagolide extended-release vaginal rings administered sequentially for 4 menstrual cycles in women with moderate to severe endometriosis-related pain. In this trial, a menstrual cycle is considered the period from day 7 of return of menses (RM+7) in a cycle until the following day 7 of return of menses in the next cycle. Visits on RM+7 can be scheduled on RM+6-10, i.e. day 6 to day 10 of return of menses.

The trial consists of the following periods:

- 1) Screening: starting immediately after the signing of the informed consent(s) and including a run-in period of two complete menstrual cycles (cycles -2 and -1)
- 2) Part A: double-blind, placebo-controlled treatment with three doses of quinagolide extended-release vaginal ring administered sequentially for four menstrual cycles (cycles 1, 2, 3 and 4)
- 3) Part B: double-blind, extension treatment with three doses of quinagolide extendedrelease vaginal ring administered sequentially for four menstrual cycles (cycles 5, 6, 7 and 8)
- 4) Follow-up: post-treatment follow-up period of two menstrual cycles (cycles 9 and 10)

Statistical Analysis Plan	Version: 1.0	FERRING
Quinagolide	31MAY2022	PHARMACEUTICALS
FE 999051 trial 000165	CONFIDENTIAL	Page 11 (44)

Abbreviations: B&B=Biberoglu and Behrman Scale, BTM=bone turnover markers, E2=estradiol, Echo=echocardiography, ECG=electrocardiography, EHP-30=Endometriosis Health Profile-30 Questionnaire, LH=luteinizing hormone, LH+7=7 days after LH surge, NRS=Numerical Rating Scale, P4=progesterone, PGIC=Patient Global Impression of Change, PGIS=Patient Global Impression of Severity, PG=pharmacogenetic(s), PK=pharmacokinetic(s), QICD=questionnaire for impulsive-compulsive disorders, QVR=quinagolide vaginal ring, RM=return of menses, RM+7=day 7 of return of menses, TVU=transvaginal ultrasound

- In case of technical issues at the start of the run-in period, subjects are allowed to re-start e-Diary recording for cycle -2. а
- Blood samples for potential endometriosis biomarkers will be collected for all subjects. If subjects provide a separate informed b consent, additional blood samples for potential analyses of circulating cell-free DNA and microRNA will also be collected. If subjects provide a separate informed consent, a blood sample for pharmacogenetic analysis will be collected. c
- ECG and Echo at screening can be arranged anytime during cycle -1 (e.g. at visit 3) but results must be available before d
- randomization. Echo at cycles 4 and 8 can be performed within ±2 weeks of visits 11 and 16, respectively. Pain impact will be assessed on both a daily and a weekly basis. e
- f
- Scoring of the worst endometriosis-related pain during the past menstrual cycle on the NRS will be performed on paper at the run-in visit. Daily scoring of endometriosis-related pain on the NRS is captured by e-Diary.
- Visits on RM+7 or LH+7 can be scheduled RM+6-10 or LH+6-9, i.e. day 6 to day 10 of return of menses or 6-9 days after LH g surge, respectively. PK visit (visit 5) can be arranged within 1-5 days of randomization (visit 4).

Screening: The screening period includes a wash-out period of approximately one month (only applicable to subjects currently using some hormonal products such as contraceptives) and a run-in period of two complete menstrual cycles (cycles -2 and -1, applicable to all subjects). Subjects who are currently using some hormonal products such as contraceptives may be eligible for the trial if they have completed the wash-out period. In this case, subjects need to sign the informed consent(s) before they discontinue those products. Discontinuation of the products should follow the labelling (e.g. completing the current cycle of contraceptives before wash-out). Subjects requiring wash-out will not be provided with the electronic diary (e-Diary) or rescue analgesics until the completion of the wash-out period, i.e. at the run-in visit.

At the run-in visit, all subjects will be asked to score the worst endometriosis-related pain from a recall of their experience during the past menstrual cycle on a self-administered 11point Numerical Rating Scale (NRS) with 0 indicating "no pain" and 10 indicating "worst imaginable pain". After standardized training of e-Diary use, eligible subjects will be instructed to record endometriosis-related pain, vaginal bleeding, occurrence of sexual intercourse and analgesic use in the e-Diary on a daily basis. Impact of endometriosisrelated pain on functioning will be assessed by subjects on both a daily and a weekly basis.

In this trial, endometriosis-related pain is evaluated as the pain located in the abdominalpelvic area and the lower back area. During the run-in period, subjects will score the worst endometriosis-related pain during the preceding 24 hours on the NRS before bedtime every night in the e-Diary.

Vaginal bleeding will be recorded as "yes" or "no" on a daily basis in the e-Diary. If there is vaginal bleeding, subjects will be asked to register their bleeding volume (spotting, light, moderate or heavy bleeding) and to answer whether they think the bleeding is related to menses or not. Based on the subject's impression of whether she has menstrual bleeding or not, the NRS score obtained for the endometriosis-related pain is assigned to dysmenorrhea (endometriosis-related pain on days with menstrual bleeding) or to non-menstrual pelvic pain (endometriosis-related pain on days with no menstrual bleeding).

Occurrence of sexual intercourse ("yes" or "no") will also be recorded in the e-Diary. In case of sexual intercourse, subjects will be asked to score the worst pain experienced during or after intercourse (dyspareunia) on the NRS. In case of no sexual intercourse, subjects will be asked if it is due to expected pain.

Rescue analgesics for endometriosis-related pain will be limited to ibuprofen and/or hydrocodone-acetaminophen in this trial. As a mild analgesic, ibuprofen will be provided to subjects in the form of 200 mg oral tablets for their use on an as-needed basis. Subjects will be instructed not to use other analgesics unless necessary. If there is a need to change analgesics, subjects should discuss with investigators, who may prescribe a strong analgesic, i.e. 5 mg hydrocodone plus 300 mg or 325 mg acetaminophen. Use of any other

analgesics for endometriosis-related pain is prohibited. Any prophylactic use of analgesics is also prohibited in this trial. Use of analgesics for endometriosis-related pain will be reported by subjects in the e-Diary on a daily basis.

The impact of the endometriosis-related pain on different aspects of functioning will be assessed by subjects both on the NRS on a daily basis and by the modified EHP-30 pain impact domain (i.e. the first 11 items plus an additional work item) on a weekly basis (The secondary endpoint of changes in the weekly impact scores is based on the original EHP-30 pain impact domain, i.e. the first 11 items. The additional work item is used only for validation.).

Part A: Subjects will be randomized into Part A of the trial on RM+7 of cycle -1 (at visit 4) if they, during the run-in period have moderate to severe endometriosis-related pain, which is defined as having a mean daily NRS score of \geq 4 for the worst endometriosis-related pain during each run-in menstrual cycle. Randomization will be performed in a 1:1:1:1 ratio to quinagolide vaginal ring dose load 360 µg at a target release rate of quinagolide 4.5 µg/day, quinagolide vaginal ring dose load 720 µg at a target release rate of quinagolide 9 µg/day, quinagolide vaginal ring dose load 1080 µg at a target release rate of quinagolide 13.5 µg/day or placebo vaginal ring for four menstrual cycles (cycles 1, 2, 3 and 4).

Part B: Subjects who have received active treatment in Part A will continue with the same doses in Part B, and those who have received placebo vaginal ring in Part A will be reallocated in a pre-determined 1:1:1 ratio to quinagolide vaginal ring dose load 360 μ g, 720 μ g or 1080 μ g at a target release rate of quinagolide 4.5 μ g/day, 9 μ g/day or 13.5 μ g/day, respectively, administered for four menstrual cycles in Part B (cycles 5, 6, 7 and 8).

Follow-up: Subjects who complete both Part A and Part B will be followed up for two menstrual cycles (cycles 9 and 10).

From randomization to follow-up (cycle 1 to cycle 10), subjects will continue to use an e-Diary to score the endometriosis-related pain, to register vaginal bleeding pattern, occurrence of sexual intercourse and the analgesic use as well as to assess the impact of the worst endometriosis-related pain on functioning, as they have done in the run-in period.

During the treatment period (Part A and Part B), subjects will self-insert the assigned ring in the upper part of the vagina on RM+7 of cycle 1 to cycle 8 at the clinic by following standard instructions for use. Supervision by the site staff can be provided if needed. After insertion, the vaginal ring will be kept in the vagina continuously for one menstrual cycle until being replaced with the next ring on RM+7 of the next cycle when the subject visits the clinic. Acceptability of the ring will be assessed by subjects via a ring acceptability questionnaire at each RM+7 visit during the treatment period. Unless under other effective birth control permitted by protocol, subjects will be required to use a non-hormonal singlebarrier contraception (i.e. condom) from wash-out (if applicable) or run-in to end-of-trial. Contraception counselling and condoms will be offered to subjects throughout the trial.

B&B will be administered electronically at randomization, at cycles 4 and 8, with trained trial coordinators completing the first part based on subjects' verbal responses and investigators completing the second part based on findings of a pelvic examination. Subjects will complete the electronic version of the EHP-30 questionnaire at randomization, and at every cycle from cycle 1 to cycle 8. PGIS scale will be completed electronically by subjects at cycle -2, at randomization and at cycles 4 and 8, while PGIC scale will be completed electronically at cycles 4 and 8.

Blood samples will be collected throughout the trial for the purpose of evaluating midluteal phase endocrine parameters, bone turnover markers, endometriosis biomarkers, quinagolide and metabolites, and routine safety laboratory parameters. In this trial, midluteal phase is defined as 6-9 days after luteinizing hormone (LH) surge (LH+6-9) as tested by subjects at home by means of commercially available urinary LH kits. LH+7 visits can be scheduled on LH+6-9, either based on an actual LH surge date as indicated by a positive LH surge test or based on an estimated LH surge date according to subjects' cycle length if subjects fail to detect the LH surge. The exact cycle day of the LH+7 visit will be derived based on the first menstrual bleeding date of the current cycle confirmed at the RM+7 visits. A full endocrine panel including estradiol, progesterone, prolactin, TSH and IGF-1 will be assessed at the mid-luteal phase of cycles -1, 1, 4, 8 and 10. Evidence of ovulation will be evaluated by serum levels of mid-luteal progesterone. A partial endocrine panel consisting of estradiol and progesterone only will also be assessed at RM+7 visits of cycles 4 and 8. Fasting blood samples for the analysis of a bone formation marker (s-PINP) and a bone resorption marker (s-CTx) will be collected during cycles -1, 4 and 8. Blood samples for endometriosis biomarkers including, but not limited to, VEGF, PIGF, IL-6 and sFlt-1 will be collected during cycles -1, 4, and 8. At the same time points, if subjects have provided a separate informed consent, additional blood samples for potential analyses of circulating cell-free DNA and microRNA will also be collected. Routine safety laboratory tests for clinical chemistry and hematology parameters will be performed during cycles -1, 4, 8 and 10. Quinagolide and metabolites will be measured within 1-5 days of first ring insertion, at both LH+7 visits and RM+7 visits of cycles 1, 4 and 8 as well as at RM+7 visits of cycles 3 and 7. Blood samples should be taken prior to ring removal at RM+7 visits. If subjects have provided a separate informed consent, a blood sample for pharmacogenetic analysis will also be collected.

ECG and echocardiography will be performed to monitor cardiovascular safety. ECG will be assessed prior to randomization during cycle -1, at cycles 4 and 8 (prior to or at visit 4, at visits 11 and 16). ECG must be performed after vital signs but before blood sampling as applicable. ECG and echocardiography at screening can be arranged anytime during cycle -1, e.g. at LH+7 visit but results must be available prior to randomization.

Echocardiography at cycles 4 and 8 can be performed within ± 2 weeks of end-of-cycle 4 visit and end-of-cycle 8 visit, respectively.

A modified questionnaire for impulsive-compulsive disorders will be completed electronically by trained trial coordinators based on subjects' verbal response prior to randomization at cycle -1, at cycles 4 and 8.

A urine pregnancy test will be performed at each clinic visit (except for the PK visit during cycle 1) throughout the trial. If the test result is positive and is confirmed by a following serum β hCG test, the subject should be discontinued from the trial. Urinalysis is performed at the run-in visit, at cycles 4 and 8.

The self-assessments of NRS, occurrence of sexual intercourse, the impact of pain, vaginal bleeding and analgesics use will be done by the subjects in the e-Diary. The daily e-Diary should be completed by the subjects before bedtime every night throughout the trial that is from visit 1 until the end-of-trial visit. Additional assessments of pain impact will be done in the weekly e-Diary. The weekly e-Diary should be completed at the end of each week throughout the trial that is from visit 1 to end-of-trial visit.

3.2 General Design Considerations

3.3 Determination of Sample Size

The sample size calculation is based on demonstrating superiority of Quinagolide vaginal ring compared with placebo vaginal ring on the primary endpoint of the change in mean daily NRS score for endometriosis-related pain at cycle 4. Taking into account of an interim analysis for futility at a conditional power of 5% (see section 11) and assuming that the standard deviation of the change in mean daily NRS is 1.5, a sample size of 52 evaluable subjects per group (in total 208 subjects) will have at least 90% power to detect a treatment effect difference of 1.0 unit using a t-test at a 5% two-sided significance level in a pre-defined hierarchical step-down procedure, starting with testing the highest dose versus placebo. Accounting for a 25% drop-out rate as observed in a previous trial there should be 70 subjects randomized to each treatment group and in total 280 subjects should be randomized. Table 3-1 summarizes the required sample size per group for different assumptions of treatment effect difference and power.

Table 3-1 Sample Size by Treatment Effect Difference

Difference in NRS score reduction	Number of subjects per group ^a			
between	Evaluable su	ubjects	Randomiz	ed subjects ^b
quinagolide vaginal ring the highest	Power	Power	Power	Power 90%
dose group and placebo vaginal ring	80%	90%	80%	
group				
0.8	60	80	80	107
0.9	48	64	64	86
1.0	40	52	54	70
1.1	32	44	43	59
1.2	28	36	38	48

a Assuming a standard deviation of 1.5 units and accounting for an interim analysis for futility at a conditional power at current trend of 5%.

b Assuming 25% drop-out rate.

A sample size re-estimation was planned to be performed at the same time of the interim analysis based on the observed standard deviation and drop-out pattern. The sample size could have been increased to 360 subjects in total or 90 subjects per group.

4 Subject Disposition

For the reporting of subject disposition with regard to the Per-Protocol (PP) analysis set the definition of being excluded from the PP population is if the subjects cycle 4 data is exclude from the PP analysis set.

4.1 Screened subjects

Screened subjects who discontinue prior to randomization are regarded as screening failures. All subjects screened will be accounted for (in total and by trial site). The total number of screened subjects will be summarized (n and % of total number of screened subjects) by: randomized, reason for failure (inclusion /exclusion not met, withdrawal by subject, other) and all.

4.2 Subject disposition

Subject disposition with respect to analysis sets (Safety, ITT, and PP) will be summarized by treatment.

4.3 Subject disposition and completion

Subject disposition with respect to analysis sets (Safety, ITT, and PP) and completion of treatment and follow-up will be summarized. Completion of treatment will be based on the end of treatment form and the timing of the potential discontinuation (is end-of cycle 4 visit performed or not), and completion of follow-up will be based on the end of trial form.

4.4 Subject completion/discontinuation

Completion of treatment, and follow-up will be defined as in the subsection 4.3.

Based on the ITT analysis set subjects completion by end of treatment and follow up, will be summarised: completed, discontinued (primary reason for discontinuation according to end of treatment form), by treatment.

4.5 Listing

The subjects screened but not randomized/allocated to treatment will be presented with the reason(s) for screen failure in a data listing.

Based on the ITT analysis set subject disposition with respect to analysis sets will be listed sorted by site, treatment and subject. Subjects who discontinued from the trial will be listed sorted by site, treatment, and subject including information on timing of and reason for discontinuation.

5 **Protocol Deviations**

Protocol deviations will be rated as either minor or major. Protocol deviations impacting the primary endpoint and thereby affecting the conclusions of the trial will in this SAP be rated as major. Major protocol deviations will lead to exclusion of data from the PP analysis set. Data will not be excluded from the data analysis in case of minor protocol deviations.

The list of major protocol deviations includes, but is not restricted to:

- Treatment received not in accordance with randomization (only data after the occurrence of the mistake to be deleted)
- Non-compliance with IMP treatment regimen for >20% of days during a non-menstrual period (only data after the first occurrence of non-compliance to be deleted)
- Missing >20% of days of e-Diary recordings during a menstrual cycle (only data of this cycle to be deleted from the respective by-cycle PP analysis)
- Use of prohibited analgesics for >1 day during a menstrual cycle (only data of this cycle to be deleted from the respective by-cycle PP analysis)

Unforeseen deviations deemed to impact the primary endpoint of the trial may additionally be rated as major protocol deviations by the Ferring clinical team on the basis of a blinded review of data before declaration of clean-file and lock of database.

The list of major protocol deviations will be detailed and documented in the clean file document prior to database release.

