#### The question to be answered is:

If the subject did not answer the diary yesterday:

14. Please let us know why you did not complete the diary yesterday.

- $\Box$  I was in too much pain from endometriosis
- □ I forgot
- $\Box$  Other reason

The answer to this question will be used to impute scores for missing data (section 9.6.1). The complete e-Diary including instructions and questions are available in Appendix 1.

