In order to control the overall type I error at 5%, a step-down procedure will be implemented. The testing sequence starts with testing the null hypothesis for the high dose against placebo  $(H_0^{Pl})$ , and if superiority is established for the high dose  $(p^{Pl} \le 0.05)$ , the testing will continue by testing the null hypothesis for the medium dose  $(H_0^{P2})$ . Again if superiority is established for the medium dose  $(p^{P2} \le 0.05)$ , the testing will continue by testing the null hypothesis for the low dose  $(H_0^{P3})$ . All the testing will be done at the 5% significance level. If any of the active treatment groups are stopped for safety reasons during the trial, the testing sequence starts with the highest remaining dose.

The primary analysis is based on observed cases (including those missing due to too much endometriosis-related pain) in the ITT population.

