### **Sensitivity Analyses**

The following sensitivity analyses will be conducted:

- 1. To test efficacy in more perfect conditions:
  - The primary analysis in the PP population using observed cases (including those missing due to severe endometriosis-related pain)
- 2. To test sensitivity to missing data:
  - The ITT analysis without assuming a NRS of 10 on days when subjects were in too much pain to complete the e-Diary

- The ITT analysis based on last-observation-carried-forward (LOCF) method
- The ITT analysis based on baseline-observation-carried-forward (BOCF) method
- The ITT analysis using multiple imputation for missing data in a placebo-based pattern mixture model (based on a missing-not-at-random condition) as described by Ratitch
- 3. To test for heterogeneity of effect:
  - The ITT analysis testing for treatment by baseline percentage of days on rescue analgesics interaction. This will be done by type of rescue analgesics
  - The ITT analysis testing for treatment by baseline mean daily NRS score interaction
- 4. The primary analysis using the actual treatment rather than the planned treatment
- 5. To test the sensitivity to adjustment in the statistical model:
  - The ITT analysis also adjusting for the percentage of days on rescue analgesics by type at cycles 1, 2, 3, and 4 (time dependent)
  - The primary analysis with the baseline defined as the average NRS score for endometriosis-related pain of the last run-in cycle (cycle -1)

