6.2 Per Protocol Analysis Set

The PP analysis set is defined as all data from the ITT analysis set except data excluded due to major protocol deviations as defined in section 5. As defined in section 5 some protocol violations will lead to exclusion of parts of a subject's data, not the entire subject.

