9.1.3 Missing data for daily worst endometriosis-related pain question

If the subject do not complete the daily diary, then the day after the subject will be asked question 14 in the e-Diary. If the answer to question 14 is "I was in too much pain from endometriosis", the missing data for the previous day will be assigned a NRS of 10 for worst endometriosis-related pain (taking a worst-case approach). Otherwise, the daily score remains to be missing.

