9.1.4.1 The mean daily NRS score for worst endometriosis related pain

For each cycle, at least 50% of the NRS scores are required to be observed (including the imputed values as described in subsection 9.1.3) for both the menstrual period and the non-menstrual period (as defined in subsection 9.1.2) to be allowed to calculate the mean daily NRS score for that particular cycle. So if above 50% of the daily NRS scores are missing in either period of that cycle, the mean daily NRS score for worst endometriosis related pain for that cycle should be missing.

As missing daily NRS scores may not be appropriately balanced across menstrual period and non-menstrual period, the mean daily NRS score will be weighted by the lengths of the menstrual period and non-menstrual period to adjust for this potential imbalance.

So the mean daily NRS score is calculated as

$$\frac{l_{mp}\overline{x}_{mp} + l_{non-mp}\overline{x}_{non-mp}}{l_{mp} + l_{non-mp}}$$

Where l_{mp} is the number of days in the menstrual period of the cycle (as defined in subsection 9.1.2), l_{non-mp} is the number of days in the non-menstrual period of the cycle in question (as defined in subsection 9.1.2), \bar{x}_{mp} is the mean daily NRS score based on the observed daily NRS scores (question 1) during the menstrual period (including imputations as described in 9.1.3), and \bar{x}_{non-mp} is the mean daily NRS score (question 1) based on the observed daily NRS scores during the non-menstrual period (including imputations as described in 9.1.3).

If the subject does not have a menstrual period in a cycle the mean daily score is calculated as a simple mean, however if more than 50% of the daily NRS scores are missing the mean daily NRS will be considered missing

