9.3 General Considerations

All efficacy endpoints will be summarised by treatment using descriptive statistics. Categorical data will be summarised using numbers and percentages (n and % of all observed) in addition to the sum 'All', the percentages are based on the total number of subjects with a corresponding assessment in the analysis set. Continuous data will be presented, using the number of subjects (n), mean and standard deviation, median, 25th percentile, 75th percentile, minimum, and maximum. The primary endpoint will be summarized using both the ITT population and the PP population, all other endpoints will be summarized using only the ITT population.

As the trial has been prematurely discontinued, it has been decided, due to the low number of subjects, that no statistical analysis will be performed, see section 1 and 12.

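### The per-protocol 20% missing-diary rule makes no exception for days missed through too much pain, which the plan elsewhere scores as 10 and counts as observed

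*SAP*

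**What the plan says.** **The deletion rule.** The third bullet of SAP section 5 lists as a major deviation "Missing >20% of days of e-Diary recordings during a menstrual cycle", and removes that cycle from the by-cycle PP analysis. Protocol 9.3 has the same rule in the same words. Neither place mentions the reason for the missing entry. SAP 6.2 builds the set from it: "The PP analysis set is defined as all data from the ITT analysis set except data excluded due to major protocol deviations". Under SAP section 4, a woman whose cycle 4 data are removed is reported as excluded from PP. SAP 5.1 and 5.2 tabulate and list the deviation.

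**Days missed through pain.** The next evening's diary asks "Please let us know why you did not complete the diary yesterday". If the answer is too much pain, SAP 9.1.3 states that "the missing data for the previous day will be assigned a NRS of 10 for worst endometriosis-related pain". For the cycle mean, SAP 9.1.4.1 then requires, in both the menstrual and the non-menstrual period, that "at least 50% of the NRS scores are required to be observed (including the imputed values as described in subsection 9.1.3".

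**Which analyses include them.** Protocol 9.6.2 says of the ITT analysis: "The primary analysis is based on observed cases (including those missing due to too much endometriosis-related pain) in the ITT population". Its list of sensitivity analyses has the matching PP entry: "The primary analysis in the PP population using observed cases (including those missing due to severe endometriosis-related pain".

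**Use of PP.** Protocol 9.6.1 calls the PP analysis of the primary endpoint supportive. SAP 9.3 keeps it as a description: "The primary endpoint will be summarized using both the ITT population and the PP population". All other endpoints are summarised in ITT only.

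**The concern.** A day missed through pain can never acquire a diary recording, because protocol 10.3 bars entry after the window closes at 2 am. The score of 10 comes from the following day's answer. The 50% rule counts scores and expressly includes these days. The 20% rule counts recordings and includes nothing. A programmer following the text would count pain-missed days as missing in one rule and observed in the other.

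The primary endpoint is pain. When days too painful for the diary help to remove the cycle that contains them, retention in PP depends partly on the outcome being summarised. It also means that a woman can be labelled a major deviator, and dropped from the PP count if the cycle is cycle 4, for a reason the plan elsewhere treats as valid high-pain data. PP is the only population besides ITT in which the final SAP shows the primary endpoint.

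**Working it through.** The plan gives no figure on this point to reproduce. The check is a day count followed by the SAP 9.1.4.1 cycle mean.

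**Inputs from the documents:** the 20% limit (SAP 5, protocol 9.3); a score of 10 for a pain-missed day (SAP 9.1.3); the weighted cycle mean and 50% rule (SAP 9.1.4.1); cycle lengths of 24 to 35 days (inclusion criterion 11, a run-in requirement used here as the range).

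**Assumed for illustration:** a 28-day cycle with 5 menstrual days at NRS 7 and 23 other days at NRS 4.

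**1. Missing days that exceed the limit:** floor(0.20 × L) + 1.

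| Cycle length L | 0.20 × L | Days needed | Share missing |
|---|---|---|---|
| 24 | 4.8 | 5 | 20.8% |
| 28 | 5.6 | 6 | 21.4% |
| 35 | 7.0 | 8 | 22.9% |

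**2. Just under the limit.** Five pain-missed days of 28 is 17.9%, so the cycle stays in PP. With 2 menstrual and 3 other days scored 10, the mean is (3×7 + 2×10 + 20×4 + 3×10)/28 = 151/28 = 5.39. The protocol 9.6.2 statement is met here.

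**3. Just over the limit.** Six isolated pain-missed days (2 menstrual, 4 other) is 21.4%. Every day has a score, so the 50% rule is fully met and ITT keeps the cycle with mean (3×7 + 2×10 + 19×4 + 4×10)/28 = 157/28 = 5.61. Across other splits of the six days the mean runs from 5.29 to 5.82. The recorded-day scores alone give (5×7 + 23×4)/28 = 127/28 = 4.54. The deleted cycle is therefore 157/28 − 127/28 = 30/28 = 1.07 points higher than its recorded days suggest. The literal 20% rule deletes it.

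**4. Mixed causes.** Five forgotten days of 28 (17.9%) are tolerated. One further day missed through pain makes 6 of 28 (21.4%), and the cycle goes. If the pain day counted as recorded, the count would stay at 5 of 28 and the cycle would stay.

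**5. Runs of missed days.** The reason question covers only the previous day, so a run of consecutive missed days yields at most one imputed 10. Six in a row leave 5 of 28 (17.9%) missing if the imputed day counts as recorded, and the cycle is kept under the 20% rule. Seven in a row leave 6 of 28 (21.4%), and it is still deleted. The six imputed days in step 3 must therefore be six separate misses, each followed by a completed diary.

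**6. Size in an arm.** If a fraction f of an arm had a cycle like step 3 and the rest averaged 4.54, deletion would lower the PP arm mean relative to ITT by 1.07 × f: 0.02, 0.05 and 0.11 points for f of 2%, 5% and 10%. These fractions are assumptions.

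**7. Effect on a difference between arms:** 1.07 × (f in placebo − f in active). With 10% and 2% it is 1.07 × 0.08 = 0.09 points, making the PP difference smaller. With the fractions reversed it is 0.09 points the other way. With equal fractions it is zero.

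**The case against.** **The rule is silent, not hostile.** Nothing in it says that imputed days count as missing. SAP 9.1.3 fills the day and leaves only the others missing, so a reader could treat a day scored 10 as not missing. This stands as an alternative reading. But the rule speaks of recordings, and the authors wrote the inclusion into the 50% rule and not here, so the literal reading is the more natural one.

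**A reader might infer that the SAP contradicts the protocol.** The documents do not support that. The SAP bullet repeats protocol 9.3, and the protocol 9.6.2 statement can be met within every cycle that PP retains (step 2). The tension lies inside the protocol, arises only for cycles over the limit, and is carried into the SAP.

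**A reader might also infer that PP drops the worst-pain cycles.** That is too broad. A high-pain cycle with completed diaries stays in, whatever its mean.

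**The strict rule may be a deliberate choice.** The protocol presents PP as efficacy under more perfect conditions. A missed diary also loses the bleeding and analgesic answers, and the two rules serve different purposes: whether a mean can be calculated, and whether the cycle was well documented. This has force. It is weakened because only the primary endpoint is summarised in PP, and because SAP 9.1.2 takes menstrual dates first from the visit log. If strictness is intended, the plan should say so and reconcile it with protocol 9.6.2.

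**The consequence is modest.** The trial ended early, no statistical analysis is planned, and ITT is shown alongside. This stands in full.

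**Conclusion.** The 20% rule needs a clarification. As written it lacks the provision for pain-missed days that the 50% rule has, and applied literally it makes PP deletion depend partly on the outcome for cycles that such days push past 5 of 24, 6 of 28 or 8 of 35 missing days. What turns on it is PP membership, the deviation and disposition tables, and the descriptive PP summary of the primary endpoint. ITT is unaffected by the 20% rule and keeps these cycles whenever the 50% rule is met.

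It may be tempting to conclude that the PP treatment difference is biased towards zero. The documents do not support this: it assumes an effective drug and more pain-missed days on placebo, and it concerns an estimate that the final SAP no longer plans. Neither the size nor the direction of any shift can be known, because no frequency of pain-missed days is given. The shifts of 0.02 to 0.11 points in an arm mean rest on the assumed cycle and the assumed 2% to 10% of women affected. This is a low-cost improvement to a supportive table.

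**What to change.** Add to the third bullet of SAP section 5: *days assigned NRS 10 under 9.1.3 count as recorded days for the 20% rule*. Derive PP membership, the deviation table and listing, and the PP disposition count on that basis. State that the sentence interprets protocol 9.3 and is consistent with 9.6.2; protocol 9.3 leaves the detailed criteria to the SAP. The decision should also be recorded in the clean file document that SAP section 5 requires before database release.

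The cost is one sentence and a small programming change, with no new data. There are two downsides. Retained cycles may lack bleeding and analgesic entries on the imputed days, so use of a prohibited analgesic on such a day might go unseen in the diary. And because the reason question reaches back one day only, runs of consecutive pain-missed days are only partly rescued (step 5).
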